3.0 SUBJECT RECRUITMENT AND SELECTION

This is a best available therapy/compassionate use study designed to determine the palliative benefit and toxicity of ¹³¹I-MIBG in patients with progressive pheochromocytoma (PHEO) or paraganglioma (PGL) who are not eligible for therapies of higher priority. Patients may receive a range of doses depending on stem cell availability and tumor involvement of bone marrow. Response rate, toxicity, and time to progression and death will be evaluated. All eligible patients will be offered participation in this study regardless of gender or race.

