- **4.53** To receive a subsequent course at > 12 mCi/kg or > 500 mCi (\pm 10%), a patient must have cryopreserved hematopoietic stem cells available in sufficient quantity, as stated in 3.14.

5.0 **REQUIRED OBSERVATIONS**

Required observations listed are for toxicity and response monitoring. More frequent or additional tests should be ordered as clinically indicated.

Observation	Before or at Entry	Day 0-7 ¹	Day 7-56	Day 56-120
Physical Exam	Х			X
CBC with Diff, Platelet count	Х		Weekly ²	X
Urinalysis	Х			X
AST, ALT, T. Bilirubin, Albumin	Х		Weekly	X
BUN, creatinine	Х		Weekly	Х
Electrolytes	Х			X
Ca, Mg, Phos	Х			X
FT ₄ , TSH	Х			X
Serum β-HCG ³	Х			
Bilat BM Asp/Bx	Х			X ⁵
Tumor Imaging (CT or MR) ⁴	Х			Х
¹³¹ I-MIBG Infusion		Day 0		
MIBG Diagnostic Scan (REQUIRED)	Х			Х
MIBG whole body scan		Between D 3-7		
Urine fractionated catecholamines & metanephrines and	X^4			X

serum chromogranin A

- 1. No routine bloodwork or radiologic studies are required while patient is hospitalized in radiation protected environment unless clinically indicated. Patients with prior electrolyte imbalance should be monitored during the hydration.
- 2. Twice weekly CBC/Diff/Plt until ANC $>500/mm^3$ & Plt count > 20,000 x 3 days without transfusion.
- 3. Obtain for females 10 years of age and older or post-pubertal.
- 4. Tumor imaging = CT/MRI as needed for optimum visualization of all areas of bulk tumor (primary & metastasis). Must be performed ≤ 6 weeks prior to study entry. Repeat urine fractionated catecholamines & metanephrines and serum chromogranin A only if elevated pre-therapy. If the patient receives further therapy on other protocols at ANY TIME POINT, no further tumor studies will be subsequently required for this protocol.
- 5. BM aspirate/biopsy must be repeated only if positive at study entry

5.1. Recommended follow up observations:

CBC with differential and platelet count, ALT, AST, bilirubin, T_4 , TSH and MIBG scan every 3 months until 1 year post treatment, then q 6 months until progression, death or other therapy. Other disease evaluation as clinically indicated.

6.0 **RESPONSE CRITERIA**

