All patients who are registered will be accounted for in the report of the results. Patients who complete one course of therapy will be evaluated for response at 2-4 months post treatment, or earlier if proceeding to other therapy. Volumetric measurable disease will be assessed with the same modality (MRI or CT scan) as was performed at the on study evaluation. The following disease status definitions will be used.

RECIST RESPONSE CRITERIA used for measurable soft tissue tumor

Overall response:

Response	Primary Tumor*	Metastatic Sites* [#]
CR	No Tumor	No tumor; catecholamines, metanephrines and chromogranin A all normal.
PR	Decreased >50%	All measurable sites decrease by $> 50\%$. Bones and bone marrow: number of positive bone sites decreased by $>50\%$; bone marrow tumor decreased by 50%

MR	No new lesions; >50% reduction of any measurable lesion (primary or metastases) with $<50\%$ reduction in any other; $<25\%$ increase in any existing lesion.
NR	No new lesions; <50% reduction but <25% increase in any existing lesion.
PD	Any new lesion; increase of any measurable lesion by >25%; previous negative marrow positive for tumor.

*Evaluation of primary and metastatic disease as outlined.

[#]One positive marrow aspirate or biopsy allowed for PR if this represents a decrease from the number of positive sites at diagnosis.

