7.0 STATISTICAL CONSIDERATIONS

Efficacy

This is a compassionate use protocol to be used as best available therapy for palliation in patients who are not eligible for protocols of higher priority. The endpoints to be analyzed will be progression free survival, survival, response and toxicity. The anticipated accrual is 4 patients per year with a total accrual of approximately 50 patients.

Toxicity

Because this is a group of patients with very far advanced disease, stopping rules will be in place. If there is >1 toxic death in the first 10 patients treated, or >2 in the first 20, then the protocol will be suspended and the data reviewed. All grade 3 and 4 toxicities will be recorded and reviewed every six months. If non-hematologic grade 4 toxicity is seen in >15% of patients, the protocol will be suspended and reviewed.

Sample Size Justification and Accrual

This study will provide additional safety data for FDA approval of MIBG and efficacy data. The FDA is interested in long-term safety and toxicity data, so the accrual of additional patients beyond that of the previous phase II study will allow this goal to be met. It is anticipated that ¹³¹I-MIBG will eventually be approved for commercial use in patients with metastatic pheochromocytoma and paraganglioma, and therefore prolongation of this compassionate use protocol will no longer be necessary.

Safety Analysis

Grade 3 and 4 adverse events will be coded by the NCI Common Toxicity Criteria v3 and summarized. Within each body system, the severity will be summarized, as well as worst toxicity overall for each patient.

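### Survival and PFS are named endpoints, but no vital-status follow-up is set after progression or other therapy, and no CT/MRI is scheduled after Day 120 outside retreatment

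*Protocol*

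**What the plan says.** - **Endpoints.** Section 7.0: "The endpoints to be analyzed will be progression free survival, survival, response and toxicity". Section 3.0 agrees: "Response rate, toxicity, and time to progression and death will be evaluated".
- **Required schedule.** The Section 5.0 table ends with the Day 56-120 column and is described as serving toxicity and response monitoring. CT/MRI is marked at entry and at Day 56-120 only.
- **Later schedule.** Section 5.1 is headed "Recommended follow up observations". It lists blood tests and an MIBG scan, at 3-month intervals in the first year. From the second year the interval lengthens, and the schedule has an end point: "then q 6 months until progression, death or other therapy. Other disease evaluation as clinically indicated". CT/MRI is not on the list.
- **Waiver.** Under footnote 4 to the Section 5.0 table, once a patient receives therapy on another protocol, "no further tumor studies will be subsequently required for this protocol".
- **Definition of progression.** Section 6.0 gives three routes to PD: a new lesion; "increase of any measurable lesion by >25" percent; or a previously negative marrow turning positive. Measurable disease is to be assessed by the same modality, CT or MRI, as at entry.
- **Deaths.** Sections 4.31 and 14.1 centre death reporting on the first six weeks. After that, Section 14.1 keeps expedited reporting for treatment-related deaths in patients still in the treatment phase, and exempts deaths from progressive disease from expedited reporting. Section 14.2 has any deaths reviewed every six months.

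**The concern.** A survival endpoint needs a way to learn whether each patient is alive, whatever has happened to the disease. Here the one long-term schedule stops at the first of progression, death or other therapy, and nothing replaces it. If the survival data come from that schedule, a patient leaves observation at progression, which in metastatic disease is probably when the risk of death goes up. Kaplan-Meier estimation assumes that those censored have the same outlook as those still followed. That would fail, in the direction of survival that looks too good.

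PFS has a milder problem. After Day 120 the recommended schedule can show a new MIBG-avid lesion, but growth of a known lesion is found only if someone orders CT/MRI. Progression by growth would then tend to be dated late and at irregular times.

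The protocol says the study will supply efficacy data alongside safety data for the FDA. An analysis plan could set censoring rules, but it cannot recover deaths or scan dates that were never collected, so this has to be settled in the protocol.

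**Working it through.** **Step 1. Endpoints against scheduled observations after Day 120**

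| Needed for | Component | Scheduled after Day 120? |
|---|---|---|
| Survival | Death before progression or other therapy | While Section 5.1 follow-up runs (recommended) |
| Survival | Death after progression or other therapy | No procedure given |
| PFS | New lesion | MIBG scan (recommended), if the lesion is MIBG-avid |
| PFS | Growth above 25%, by CT/MRI | No; only as clinically indicated or at retreatment |
| PFS | Negative marrow turning positive | No; footnote 5 requires a repeat only if positive at entry |

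**Step 2. How large could the survival bias be?**

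The protocol states no figure to reproduce, so this is an illustration with a three-state model (progression-free, progressed, dead) and constant hazards.

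Inputs from Section 2.2 (the earlier series): 35% progression within one year; 64% 5-year survival. From Section 7.0: about 50 patients. Assumptions that are not in the documents: the death hazard before progression, *h*; constant hazards over five years; no death after progression captured.

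Let λ be the progression hazard, μ the death hazard after progression, and a = λ + h.

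1. λ solves (λ/a)·(1 − e^(−a)) = 0.35. At h = 0.01, λ = 0.433: (0.433/0.443)·(1 − e^(−0.443)) = 0.35.
2. μ solves e^(−5a) + λ·(e^(−5μ) − e^(−5a))/(a − μ) = 0.64. At h = 0.01, μ = 0.154: 0.109 + 0.531 = 0.640.
3. With censoring at progression, the 5-year Kaplan-Meier value tends to e^(−5h). At h = 0.01 this is e^(−0.05) = 0.951.
4. Expected deaths seen in 50 patients: 50·(h/a)·(1 − e^(−5a)). At h = 0.01: 50·(0.01/0.443)·0.891 = 1.0. All deaths by 5 years: 50 × 0.36 = 18.

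| Assumed h per year | True 5-year survival | Apparent 5-year survival | Deaths seen, of 18 | Still followed at 5 years |
|---|---|---|---|---|
| 0.01 | 64% | 95% | 1.0 | 11% |
| 0.02 | 64% | 90% | 2.0 | 10% |
| 0.05 | 64% | 78% | 4.6 | 8% |
| 0.089 | 64% | 64% | 7.7 | 7% |

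A simulation of 400,000 patients at h = 0.01 gave true survival of 0.640 and a Kaplan-Meier estimate of 0.950, in line with the first row.

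The last row is the break-even point: h = −ln(0.64)/5 = 0.089, where death is equally likely before and after progression. The upward bias needs only a lower death hazard before progression than after it.

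**The case against.** A reader might infer that deaths after progression are not collected and that survival **is** informatively censored. The documents do not say so. Section 5.1 limits tests and scans; it does not forbid collecting vital status and sets no censoring date. Section 6.0 promises that every registered patient will be accounted for in the report, Section 14.2 reviews any deaths, and Section 14.1 releases late deaths from progressive disease only from expedited reporting. Censoring rules commonly sit in an analysis plan, which is not at hand. All of that stands. What remains is that a review covers only the deaths the team hears of, and no section says how it would hear of them once Section 5.1 ends.

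A reader might also infer that PFS is not measured by the protocol's own definition. That goes too far. A new lesion is PD and can show on the recommended MIBG scans; one post-treatment CT/MRI is required at Day 56-120; more are allowed when clinically indicated; and retreatment under Section 4.5 calls for the pre-treatment evaluation again (15 of 50 patients in the earlier series had more than one treatment). Footnote 4 removes a requirement for tumor studies; it does not prohibit them.

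The figures of 95%, 90% and 78% are no forecast. Each equals e^(−5h) for an assumed h, in the worst case where no later death is ever captured. The share still followed at 5 years extends first-year progression at a constant rate, which Section 2.2 does not support beyond year one.

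Finally, this is a compassionate-use study whose primary aims are palliation and toxicity. No hypothesis, comparator or decision rule rests on survival or PFS. That limits the consequences, but both remain endpoints the protocol says it will analyze.

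**Conclusion.** The point holds as a gap in data collection. Survival and PFS are endpoints, yet after Day 120 the protocol offers only a recommended schedule that ends at progression or other therapy. It provides no vital-status follow-up beyond that and no scheduled CT/MRI outside retreatment.

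Survival is therefore at risk of informative censoring. The likely direction is upward, provided death is more likely after progression than before. The size cannot be derived from the documents: under the stated assumptions the excess at 5 years runs from 31 percentage points (95% against 64%) to 14 (78% against 64%), and reaches zero at a pre-progression hazard of about 0.089 per year. Every later death that is captured shrinks it.

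PFS is incompletely measured: growth and marrow conversion are not systematically looked for after Day 120, so progression by those routes will tend to be recorded late.

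**What to change.** **Survival.** Add to Section 5.1 a required vital-status check, by phone or record, every 6 months until death, loss to follow-up or data cut-off, regardless of progression or other therapy. State that survival is time to death from any cause, censored only at the date last known alive.

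**PFS.** Keep the Section 6.0 definition of PD. Record the date and modality of every disease assessment, including clinically indicated CT/MRI. State in the protocol and the report that growth is not systematically assessed after Day 120. Report a sensitivity analysis that counts the start of other therapy as an event.

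Redefining progression on the MIBG scan alone would be a poor substitute, because it discards the growth limb of the protocol's own definition.

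**Cost.** About two contacts per patient-year for about 50 patients: at most 50 × 5 × 2 = 500 over five years each, fewer as patients die. This version adds no required scan. Making the Section 5.1 scans mandatory or withdrawing the footnote 4 waiver would add scans, and Section 8.0 bills these to third-party payers. The survival estimate will probably look less favourable, and the PFS limitation is disclosed rather than removed.

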7.0 STATISTICAL CONSIDERATIONS

Efficacy

This is a compassionate use protocol to be used as best available therapy for palliation in patients who are not eligible for protocols of higher priority. The endpoints to be analyzed will be progression free survival, survival, response and toxicity. The anticipated accrual is 4 patients per year with a total accrual of approximately 50 patients.

Toxicity

Because this is a group of patients with very far advanced disease, stopping rules will be in place. If there is >1 toxic death in the first 10 patients treated, or >2 in the first 20, then the protocol will be suspended and the data reviewed. All grade 3 and 4 toxicities will be recorded and reviewed every six months. If non-hematologic grade 4 toxicity is seen in >15% of patients, the protocol will be suspended and reviewed.

Sample Size Justification and Accrual

This study will provide additional safety data for FDA approval of MIBG and efficacy data. The FDA is interested in long-term safety and toxicity data, so the accrual of additional patients beyond that of the previous phase II study will allow this goal to be met. It is anticipated that ¹³¹I-MIBG will eventually be approved for commercial use in patients with metastatic pheochromocytoma and paraganglioma, and therefore prolongation of this compassionate use protocol will no longer be necessary.

Safety Analysis

Grade 3 and 4 adverse events will be coded by the NCI Common Toxicity Criteria v3 and summarized. Within each body system, the severity will be summarized, as well as worst toxicity overall for each patient.

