14.0 ADVERSE EVENT REPORTING AND DATA SAFETY MONITORING

14.1 Adverse Event Reporting

All patients will have toxicity monitoring for 6-8 weeks following ¹³¹I-MIBG therapy. Toxicities will be graded according to the Common Toxicity Criteria (CTC) version 3.0 (http://ctep.info.nih.gov) and attribution assigned. Toxicities will be summarized and reported annually to the FDA.

All toxicities will be categorized as either expected or unexpected. For the purposes of this trial, all unexpected Grade 4 toxicities and all deaths that occur in the first six weeks following treatment will be categorized as a Serious Adverse Event and will require expedited reporting. All toxic deaths will be reported by phone within 24 hours to the data center at UCSF and the FDA. MedWatch forms will be filed for all unexpected Grade 4 toxicities and deaths with each participating institution's IRB and the FDA. Unexpected Grade 4 toxicities and treatment-related deaths will also be reported in an expedited fashion for patients who remain in "treatment phase" after six weeks (i.e. no additional therapy). However, deaths due to progressive disease will not require expedited reporting after 6 weeks.

Other serious adverse events that are coded as unexpected Grade 2 and 3 toxicities will also be reported in expedited fashion as above. No Grade 1 toxicities will require expedited reporting.

All toxicities will be collected and summarized annually in reports to the IRB and FDA.

Grade 4 blood/bone marrow toxicities are EXPECTED and will not require expedited reporting. In addition, because Grade 3 febrile neutropenia is common, hospitalization for fever and neutropenia will be recorded but will not require expedited reporting. Grade 4 febrile neutropenia (septic shock) or any Grade 4 infection will be reported using the expedited system noted above.

Grade 4 pain due to the patients disease and/or hospitalizations to manage symptoms from the underlying disease will be recorded but not require expedited reporting.

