14.2 Data Safety Monitoring Plan

This protocol has been submitted to the FDA and the UCSF Comprehensive Cancer Center Protocol Review Committee and the Pediatric Clinical Research Center at UCSF. The study accrual and toxicity and any deaths will be reviewed every six months by the study chair, [name], along with the nurse coordinator and the statistician. Requirements for the INDs will be strictly adhered to by expedited and annual reports to the FDA.

If more than one unexpected or not-previously-described SAE attributable to study drug is observed, accrual to the protocol will be suspended. An ad hoc committee comprising the study chair ([name]), other lead investigators, and at least one subspecialist not participating in the trial will be convened by the study chair. An assessment of the risks to patients will be made, and a recommendation to continue with the study or close the trial will be made to the IRB for review. Should a decision be made to continue with the trial, the modifications to the protocol, the updated assessment of risks and benefits, and a modified informed consent will be submitted to the IRB prior to reopening the trial.

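### No toxic-death limit applies after patient 20 of about 50; later toxic deaths reach a numeric trigger only if they are unexpected or not previously described

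*Protocol*

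**What the plan says.** Protocol Section 7.0 (Toxicity) gives two numeric rules. The first counts toxic deaths: "If there is >1 toxic death in the first 10 patients treated, or >2 in the first 20, then the protocol will be suspended". The second counts severe events: "If non-hematologic grade 4 toxicity is seen in >15% of patients, the protocol will be suspended and reviewed". The Efficacy paragraph of the same section gives the planned size: "The anticipated accrual is 4 patients per year with a total accrual of approximately 50 patients". The Safety Analysis paragraph reads: "Grade 3 and 4 adverse events will be coded by the NCI Common Toxicity Criteria v3 and summarized".

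Two passages outside Section 7.0 also bear on deaths. Section 14.1 states that "all unexpected Grade 4 toxicities and all deaths that occur in the first six weeks following treatment will be categorized as a Serious Adverse Event". Section 14.2 adds a third numeric trigger, which has no patient limit: "If more than one unexpected or not-previously-described SAE attributable to study drug is observed, accrual to the protocol will be suspended". Section 14.2 also provides a periodic look: "The study accrual and toxicity and any deaths will be reviewed every six months by the study chair", together with the nurse coordinator and the statistician. No threshold is attached to that review.

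**The concern.** Section 7.0 justifies having stopping rules by how advanced the patients' disease is. That reason applies equally to patient 21 and patient 50, yet the death count stops at patient 20. Because the protocol itself fixes the rule, this is not a detail left to an analysis plan.

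The other triggers do not clearly take over:

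- **The 15% rule** names grade 4 only. Section 14.1 lists grade 4 toxicities and deaths as separate items, so a literal reader would not count a death under grade 4. The rule also excludes hematologic toxicity, while Section 9.0 calls hematologic toxicity the major risk and says that bleeding or infection from it may be life threatening.
- **The Section 14.2 trigger** depends on novelty. Section 9.0 already lists death from treatment complications as a rare risk, and Section 2.2 already describes a fatal case of acute respiratory distress syndrome (ARDS). The fatal toxicities easiest to foresee are therefore the ones most easily judged expected and already described.

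At stake is whether an excess of foreseeable toxic deaths over most of the accrual period would suspend the study by rule or only by judgement.

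**Working it through.** **Inputs from the protocol**

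- Planned accrual is about 50 patients at 4 per year (Section 7.0), so 50/4 = 12.5 years. Patient 20 enters at about 20/4 = 5 years.
- Death rule (Section 7.0): suspend at 2 or more toxic deaths in the first 10, or 3 or more in the first 20.
- 15% rule: 0.15 × 50 = 7.5, so 8 or more patients at full accrual.
- Toxic deaths on record (Section 2.2): one fatal ARDS case. 55 patients had been treated and response data are given for 50, so 1/55 = 1.8% to 1/50 = 2.0%.

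**Assumption.** The protocol gives no unacceptable toxic-death rate and no operating characteristics, so there is no stated figure to reproduce. True rates p of 2%, 5%, 10% and 15% are assumed, with independent patients and a constant rate.

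**Uncovered share.** (50 − 20)/50 = 60% of patients, or 12.5 − 5 = 7.5 years of accrual.

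**Step 1: chance that the death rule suspends.** Let X be toxic deaths in patients 1-10 and Y those in patients 11-20, each binomial(10, p). Then

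P(suspend) = P(X≥2) + P(X=0)·P(Y≥3) + P(X=1)·P(Y≥2).

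At p = 10%: 0.2639 + 0.3487 × 0.0702 + 0.3874 × 0.2639 = 0.2639 + 0.0245 + 0.1022 = 0.3906.

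**Step 2: chance of three or more toxic deaths in patients 21-50.** This is P(Z≥3) with Z binomial(30, p). At p = 10% it is 0.5886, with 30 × 0.10 = 3.0 deaths expected.

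**Step 3: joint chance that the rule stays silent and three or more deaths follow.** This is (1 − step 1) × step 2. At p = 10%: 0.6094 × 0.5886 = 0.359.

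**Step 4: illustrative continuation.** The same exact recursion is carried on with limits of >3 in 30, >4 in 40 and >5 in 50. These limits are an assumption, not protocol text.

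| True rate | 1: suspends as written | 2: ≥3 deaths in 30 | 3: silent, then ≥3 deaths | 4: suspends if continued to 50 |
|---|---|---|---|---|
| 2% | 2.0% | 2.2% | 2% | 2.1% |
| 5% | 12.0% | 18.8% | 17% | 15.3% |
| 10% | 39.1% | 58.9% | 36% | 56.3% |
| 15% | 64.9% | 84.9% | 30% | 86.6% |

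Column 3 is the relevant one. Column 2 alone ignores that the early rule may already have suspended the study.

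All four columns concern the death rule only. They give no credit for the 15% rule or Section 14.2, because the protocol offers no basis for the share of toxic deaths that either would catch.

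**The case against.** A reader might infer that toxic deaths in patients 21-50 meet no numeric rule at all. The protocol does not support that. The Section 14.2 trigger runs for the whole trial, Section 14.1 makes every death within six weeks of treatment a serious adverse event, and the trigger wording is disjunctive: unexpected or not previously described. A second attributable event of that kind, fatal or not, suspends accrual. The generic risk entries in Section 9.0 do not settle whether a particular death is expected. This objection stands and narrows the gap to attributable deaths judged both expected and already described.

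A reader might also infer that fatal cases vanish from reporting. That goes too far. The Safety Analysis also promises each patient's worst toxicity overall, with no grade cap in that phrase. Survival is an analysed endpoint, and Section 14.1 requires toxic deaths to be phoned to the data center and the FDA within 24 hours. The grade 3 and 4 wording is loose, but it does not suppress deaths. Likewise, the 15% rule may have been meant as grade 4 or worse; the protocol does not say.

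Some of the case on size also stands. At rates near the recorded experience (about 2%) or at the 5% ceiling in Section 9.0's rare category, the early rule seldom trips and extension changes little. The six-monthly review sees about two new patients each time (4 per year), so deaths would be noticed. Front-loading a death boundary in a compassionate-use protocol is a design choice, not an arithmetic error.

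The objection does not supply a death limit after patient 20. Review without a threshold leaves suspension to discretion, whereas Section 7.0 made it automatic for the first 20.

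**Conclusion.** The point holds in this form: Section 7.0 limits toxic deaths only in the first 10 and first 20 of about 50 patients, and its 15% rule does not name grade 5. For the remaining 60% of accrual, a toxic death counts toward a numeric trigger only if it is an unexpected or not-previously-described event under Section 14.2. Otherwise it receives only the six-monthly review.

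The size depends on a true toxic-death rate that the protocol does not state. At 2% the gap hardly matters. At 10% the death rule misses in 60.9% of trials (1 − 0.391), and in 36% of trials it misses and three or more toxic deaths follow in patients 21-50. At 15% that joint chance is 30%; it is lower because the early rule trips more often.

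**What to change.** In Section 7.0:

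1. Extend the toxic-death boundary to the full planned accrual, and state the death rate it is meant to detect and its operating characteristics. The sponsor should choose the limits. Continuing the existing pattern, as in the last column of the table, shows what is available.
2. In the 15% rule, change grade 4 to grade 4 or 5.
3. In the Safety Analysis, change grade 3 and 4 to grade 3 to 5, so that fatal events are explicitly included.

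The cost is a few short text edits and a slightly higher chance of a safety pause at moderate toxicity. Under the illustrative limits, suspension rises by 0.1 percentage points at a 2% rate (2.0% to 2.1%) and by 3.3 points at 5% (12.0% to 15.3%). The gain is 17.2 points at 10% (39.1% to 56.3%) and 21.7 points at 15% (64.9% to 86.6%).
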